1.2.3. Toxicity

Exendin-4, the naturally occurring *Heloderma* product, has been used extensively in human studies (83-85). Side effects reported with exendin-4 have been limited, although in higher doses nausea has been reported. Exendin-(9-39) is a synthetic molecule that has also been used in multiple human studies (79; 81; 86-91). Dose ranging studies have been reported by both Schirra and Edwards (79; 81). In neither of the previous studies were adverse effects of exendin-(9-39) reported. In addition, no effects of exendin-(9-39) on blood pressure and heart rate were found on these studies. In both animals and humans studies exendin-(9-39) seems to be relatively short-lived in the circulation. While GLP-1 seems to play an important role in glucose tolerance it is not the only regulatory factor involved, and the glucose tolerance induced by exendin-(9-39) is relatively modest. In our studies, infusion of exendin-(9-39) to mice with a null mutation of the K_{ATP} channel did not significantly worsen the glucose tolerance of these mice, nor affected weight gain (16). We have not observed any serious adverse events on the subjects we have studied under this IND: to date, all doses appear to have been generally safe and well tolerated in all three populations studied. There have been no SAEs, deaths, or withdrawals due to study drug.

Toxicology studies were completed in Sprague Dawley rats (7±1 days of age) and beagle dogs (13 days of age). In 14-day non-GLP studies, three daily subcutaneous (SC) doses of 15, 50, and 150 mg/kg/dose were administered to rats and 5, 15, and 40 mg/kg/dose were administered to dogs. Based on the lack of toxicologically significant findings, doses for GLP 28-day studies were increased to 20, 80, and 300 mg/kg/dose three times daily for rats and 10, 30, and 100 mg/kg/dose three times daily for dogs. Toxicological endpoints evaluated included: clinical observations, body weight, food consumption, clinical pathology, CNS assessment (rats), electrocardiography (dogs), toxicokinetics, and histopathology. The only exendin (9-39)-related observations noted were increased serum glucose in female rats and decreased serum triglycerides in male rats. In the cardiovascular safety pharmacology study, beagle dogs (7 to 8 months old) were administered a single SC dose of vehicle or 5, 20, or 80 mg/kg exendin (9-39) in a 4 x 4 Latin-square design. No toxicologically significant findings were observed. A dose proportional increase in exendin-(9-39) plasma exposure was observed; combined average AUC_{last} on Day 28 in male and female rats at the 300 mg/kg/dose was 249,000 ng•h/mL and at the 100 mg/kg/dose in dogs was 340,500 ng•h/mL. In conclusion, based on the available data, no observed adverse effect levels (NOAELs) were 900 mg/kg/day in rats and at 300 mg/kg/day in dogs. The human equivalent intravenous dose based on body surface area and a bioavailability of 70% are 116 mg/kg/day and 102 mg/kg/day.

1.3. Findings from Pre-Clinical and Clinical Studies (see attachments)

1.3.1. Findings from Pre-Clinical Research

We have conducted experiments that showed a significant effect of exendin-(9-39) on fasting blood glucose levels in *SUR1*^{-/-} mice. Mice carrying a null mutation in the SUR-1 gene exhibit significant fasting hypoglycemia (59.4±1.5 mg/dL vs. 75±1.8 mg/dL, p=0.0000003) and glucose intolerance when compared to wild-type littermates.

To evaluate the effect of GLP-1r antagonism in mice lacking K_{ATP} channels, we treated *SUR1*^{-/-} mice with exendin-(9-39). Twelve-18 wk old male *SUR1*^{-/-} (n=22) and wild type littermates (n=23) were randomized to treatment or vehicle. The treatment group received a continuous infusion of exendin-(9-39) at a dose of 150 pmol/kg/min (0.03 mg/kg/hr) via a subcutaneous mini-osmotic pump (Alzet model 2002) for 2 wks. The control group received an infusion of vehicle (0.9%NaCl/1%BSA). On day 7, fasting blood glucose was significantly lower in vehicle-treated *SUR1*^{-/-} mice compared to vehicle-treated wild-type littermates (p=0.000002). Treatment with exendin-(9-39) significantly raised fasting blood glucose in *SUR1*^{-/-} mice compared to vehicle-treated *SUR1*^{-/-} mice (82.2±6.3 mg/dL vs. 63.2±4.9 mg/dL, p=0.03, on day 3; 82±4.7 mg/dL vs. 56.4±4.3 mg/dL, p=0.0006, on day 7). Fasting insulin/glucose ratio was increased in *SUR1*^{-/-} mice compared to wild-type littermate control mice (p=0.04) and was normalized by exendin-(9-39) treatment (WT vs. *SUR1*^{-/-}Ex-(9-39): p= 0.32), suggestive of a direct islet effect of exendin-(9-39) on insulin secretion. Insulin sensitivity determined by the measurement of blood glucose in response to an intraperitoneal injection of insulin (0.5 U/kg) was unaffected by treatment. Similarly, glucose tolerance, which is impaired in *SUR1*^{-/-} mice, was not significantly affected by treatment with exendin-(9-39) (fig. 5). Weight gain was not different in the experimental groups.

The *in vivo* studies were confirmed by perfusion studies. Islets were isolated from *SUR1*^{-/-} mice by collagenase digestion and cultured for 3 days in RPMI 1640 medium containing 10 mM glucose. Batches of 100 cultured islets were loaded onto a nylon filter in a chamber and perfused with Krebs-Ringer bicarbonate buffer with 0.25% bovine serum albumin at a flow rate of 2mL/min. Islets were perfused with a ramp of a physiologic mixture of amino acids (0-12 mM) in the presence or absence of exendin-(9-39) at a concentration of 100 nM. As previously reported (30) the *SUR1*^{-/-} islets abnormally released insulin in response to a mixture of amino acids. This response to amino acids was blocked by exendin-(9-39). The insulin response to KCl was similar in the presence and absence of exendin-(9-39). The effect of exendin-(9-39) on cAMP was determined in static incubations of isolated islets. In the absence of exogenous GLP-1, exendin-(9-39) significantly decreased basal intracellular cAMP in *SUR1*^{-/-} islets. Amino acids significantly increased cAMP levels in *SUR1*^{-/-} islets compared to baseline and this effect was significantly reduced by exendin-(9-39). In static incubations, the effect of exendin-(9-39) on cAMP levels mirrored its effect on insulin secretion, suggesting that exendin-(9-39) effects on insulin

secretion in *SUR-1^{-/-}* islets are mediated by changes in cAMP. Baseline insulin secretion was significantly reduced by exendin-(9-39). As seen in the perfusion studies, amino acids significantly increased insulin secretion in *SUR-1^{-/-}* islets and exendin-(9-39) significantly reduced amino acid-stimulated insulin secretion. Finally, we studied the effect of exendin-(9-39) on the characteristically elevated intracellular calcium concentration of *SUR-1^{-/-}* islets (30). Exendin-(9-39) did not affect basal or the amino acid-stimulated rise in calcium.

1.3.2. Findings from Clinical Research

Preliminary Studies: Exendin-(9-39) inhibits insulin secretion and elevates fasting blood glucose levels in subjects with K_{ATP} hyperinsulinism (17).

Subjects (n=9,6F) age 15-47 yrs with congenital hyperinsulinism were admitted to the inpatient unit of the CHOP CTIC. After an overnight fast, subjects received an intravenous infusion of vehicle (0.9%NaCl) for 1 hour followed by an intravenous infusion of exendin-(9-39) at three different doses [100, 300 and 500 pmol/Kg/min (0.02, 0.06 and 0.1 mg/kg/hr)] for 2 hours each or vehicle for 6 hours. All subjects underwent the vehicle and exendin-(9-39) infusions in randomized order and on different days. Blood samples for blood glucose, insulin, C-peptide, glucagon, and intact GLP-1 were obtained at multiple time points during the infusions. Exendin-(9-39) increased fasting blood glucose levels in all subjects compared to vehicle [average fasting blood glucose during study on vehicle vs. exendin-(9-39): 84 ± 12.2 mg/dL vs. 105 ± 23.2 mg/dL $p < 0.01$]. Six of the subject had hypoglycemia (blood glucose < 70 mg/dL) during vehicle infusion while none of them had hypoglycemia during exendin-(9-39) infusion. Fasting insulin to glucose ratio was significantly lower during exendin-(9-39) infusion compared to vehicle (0.08 ± 0.03 vs. 0.12 ± 0.04 , $p = 0.01$) (fig.5). Fasting glucagon and GLP-1 levels were not different during exendin-(9-39) infusion compared to vehicle. Exendin-(9-39) was well tolerated with no side effects.

The preliminary pre-clinical and clinical studies demonstrate that antagonism of the GLP-1r by exendin-(9-39): 1) suppresses insulin secretion and elevates fasting blood glucose levels in *SUR-1^{-/-}* mice; 2) suppresses baseline and amino acid-stimulated insulin secretion in *SUR-1^{-/-}* islets; and 3) suppresses insulin and elevates fasting blood glucose levels in human subjects with K_{ATP} HI. The insulin inhibitory effect seems to be mediated by the effect of exendin-(9-39) on intracellular cAMP levels in pancreatic β -cells. The effects of exendin-(9-39) on *SUR-1^{-/-}* islets in the absence of agonist stimulation suggest that the GLP-1 receptor is constitutively active in these islets. Overall, our findings suggest a potential role for GLP-1 in the pathogenesis of K_{ATP} hyperinsulinism. Clearly, the promising effects of exendin-(9-39) in the mouse model of K_{ATP} HI and in subjects with K_{ATP} hyperinsulinism suggest a therapeutic potential for GLP-1 receptor antagonism in this disorder.

1.4. Dose Rationale and Risk/Benefits

The doses used in previous human studies ranged from 30 to 900 pmol/kg/min (0.006 to 0.18 mg/kg/hr) (79; 81; 86-91). Schirra et al.(79) demonstrated that

under physiological post-prandial plasma levels of GLP-1 (achieved by an intravenous infusion) administration of exendin-(9-39) at 30 and 60 pmol/kg/min (0.006 and 0.012 mg/kg/hr) significantly reduced the glucose infusion rate required to maintain blood glucose at 140 mg/dL in normal subjects, while a dose of 300 pmol/kg/min (0.06 mg/kg/hr) totally abolished the elevated demand for exogenous glucose under the experimental conditions. Furthermore, at euglycemia, infusion of exendin-(9-39) at 300 pmol/kg/min (0.06 mg/kg/hr) significantly raised basal glucose and glucagon. Edwards et al.(81) studied the effect of exendin-(9-39) on fasting plasma glucose in normal adult volunteers. They found that exendin-(9-39) infused at a dose of 500 pmol/kg/min (0.1 mg/kg/hr) increased fasting plasma glucose significantly compared with controls infused with saline. After cessation of exendin-(9-39) infusion, the plasma glucose level in response to exendin-(9-39) dropped to that of the control. In summary, these studies demonstrated that at a dose of 300 pmol/kg/min (0.06 mg/kg/hr), exendin-(9-39), abolishes the effects of physiologic post-prandial plasma levels of GLP-1, and that a higher dose of 500 pmol/kg/min (0.1 mg/kg/hr) increases fasting plasma glucose levels in normal subjects. In these studies, exendin-(9-39) was well tolerated by all subjects and there was not effect on pulse or blood pressure. No adverse effects related to exendin-(9-39) were reported in the previously discussed studies.

[figure not shown]
In our studies in mice with a null mutation of SUR-1, a pilot study demonstrated that a dose of 150 pmol/kg/min (0.03 mg/kg/hr) was effective in increasing fasting blood glucose levels, while a lower dose of 50 pmol/kg/min (0.01 mg/kg/hr) did not have an effect. In our pilot human studies, we have used a dose ranging from 100-500 pmol/kg/min (0.02-0.1 mg/kg/hr). From these studies the higher dose (500 pmol/kg/min) was given at the end of the infusion elevating blood glucose levels after a long fast (18 hrs). These doses were well tolerated. We have studied 2 neonates at this dose level administered over 6 hrs and did not find an effect on glucose infusion rates.

We developed a specific and sensitive LC-MS/MS method to quantify the concentration of exendin-(9-39) in human plasma (82) and measured exendin(9-39) concentration serially in individuals who participated in our research studies and received exendin-(9-39) intravenously. A total of 202 PK observations from twenty-six adult and pediatric subjects were included in the analysis. The final parameter estimates were obtained using FOCE with interaction method in NONMEM (version 7.3). A linear two-compartment model best described the observed data, and the PK parameters were estimated with good precision (%CV<50). The PK parameters were related to body weight and age. Gender and creatinine clearance did not affect the clearance of exendin-(9-39) in the studied population. Typical clearance and elimination half-life for pediatric population with median weight 5 Kg are 1.64 L/hr and 0.94 hr, respectively.

The final model parameters are presented in the table below:

PARAMETERS	Population Mean (SE)	Population Variance (%CV)
CL (L/hr)	11.9 (0.781)	0.0722 (0.0309)
VC (L)	8.57 (0.925)	-
Q (L/hr)	3.85 (1.36)	-
Vp (L)	7.00 (1.24)	-
σ _Proportional error	0.310 (0.0381)	-

Based on our clinical data to date including the observed and modeled PK data, we are proposing additional dose-escalation cohorts starting with a dose that is 2-fold higher than the highest dose used in the pilot study [1000 pmol/kg/min (0.2 mg/kg/hr)] up to a maximum dose that is lower than the human equivalent (assuming 70% bioavailability) NOAELs from the toxicology studies in rats and dogs. The estimated range of AUC (A) and C_{Max} (B) with these doses were simulated using the developed population PK model and are shown as follows:

The dotted line is the exposure of the NOEL dose in dog. The dashed line is the exposure of the NOEL dose in rat. AUC0-inf = Area under the concentration-time curve from time=0 to infinity; Number of simulated subject = 1000; Open circle = Median; Error Bar = 95 % percentile

Clinical and nonclinical pharmacokinetic parameters and safety factors are summarized in the following table.

Study Type	Dose (mg/kg/hr)	C_{max} (ng/mL)	AUC (ng*hr/mL)
Proposed in Neonates	0.2	69.45 ^a	625.5 ^a
Proposed in Neonates	0.6	208.3 ^a	1876 ^a
Proposed in Neonates	2	694.5 ^a	6255 ^a
Proposed in Neonates	6	2083 ^a	18764 ^a

Rat (Study #13835B)	900 mg/kg/day (300 mg/kg TID)	63200 ^b	249,000
Dog (Study #13835D)	300 mg/kg/day (100 mg/kg TID)	49500 ^c	340,500

^a – median value of 1000 simulated subjects; ^b – represented Cmax value of male rats following a single dose administration; ^c – represented Cmax values of female dogs on Day 28

Safety Margins based on dose and exposure (AUC)

Proposed dose rate (mg/kg/hr)	Total dose over 9 hours ^a (mg/kg)	Safety margin based on HED from rat (300 mg/kg/day) ^b	Safety margin based on HED from dog (900 mg/kg/day) ^b	Safety margin based on Cmax from rat (63200 ng/mL) ^c	Safety margin based on Cmax from dog (49500 ng/mL) ^d	Safety margin based on AUC from rat (249000 ng*hr/mL)	Safety margin based on AUC from dog (340500 ng*hr/mL)
0.2	1.8	57	65	910	713	398	544
0.6	5.4	18	22	303	238	133	181
2.0	18	5.6	6.5	91	71	40	54
6.0	54	1.9	2.2	30	24	13	18

^a – Assuming infusion over nine hours is the daily dose

^b – For rat HED is 102 mg/kg/day; for dog HED is 117 mg/kg/day; calculations includes bioavailability of 70%

^c – represented Cmax value of male rats following a single dose administration; ^d – represented Cmax values of female dogs on Day 28

Exendin -(9-39) will be administered intravenously as in the previous human studies. In short-term infusions studies Schirra (79) and Edwards (81) did not find a cumulative or persistent effect once the infusion was discontinued. No adverse effects of exendin-(9-39) were reported in the previously discussed studies. Exendin-(9-39) was well tolerated by all subjects and there was not effect on pulse or blood pressure.

In the children, adolescents and adults with congenital hyperinsulinism that we have studied to date, all doses appear to have been generally safe and well tolerated in all three populations studied. There have been no SAEs, deaths, or withdrawals due to study drug. Adverse events, regardless of causality, were reported in 19 of the 31 subjects (61.3%) treated to date. Treatment-related AEs were reported in only 3 subjects (9.7%). The most common adverse event observed as expected in this population was hypoglycemia (16 of 31 subjects, 51.6%); the majority of these events were Grade 1 or 2 and all were assessed as unrelated to investigational drug. Adverse events possibly related to the investigational drug included emesis (Grade 1) in one subject and transient hyperglycemia in two subjects (Grade 3). The occurrence of adverse events was balanced between the investigational drug and vehicle conditions.

Other than the effects on glucose homeostasis, which appears to be transient in human subjects, we do not anticipate other effects. Therefore, the anticipated benefits derived from these experiments which includes our understanding of the

physiopathologic role of GLP-1 in congenital hyperinsulinism, and moreover, the potential effect of exendin-(9-39) in controlling the severe hypoglycemia affecting these patients in face of the lack of effective medical therapy justify the proposed studies.

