6. Feedings: Infants will be allowed to continue feedings by mouth or by nasogastric/gastrostomy tube. Feedings will be continued every 3 hours and the volumes offered will be maintained equal during the two 9 hr study

- periods. The volume taken with each feeding will be recorded. Only intravenous glucose will be adjusted to maintain euglycemia.
7. Randomization: The investigational drug services will assign the order of the studies by randomization. They will inform the PI, study coordinator, and CTSC.
 8. Intravenous infusion of exendin-(9-39) and vehicle. All subjects will receive an infusion of exendin-(9-39) and vehicle for 9 hours on two separate days and in random order. Exendin-(9-39) /vehicle will be infused intravenously over a period of 9 hours starting at approximately the same time \pm 90 minutes on each day. The starting dose of exendin-(9-39) will be 1000 pmol/kg/min (0.2 mg/kg/hr). The dose will be escalated as outlined below. The volume of saline to be infused will be calculated to match the volume rate of exendin-(9-39).
 9. Post-infusion follow-up for subjects who have been able to discontinue dextrose infusion. Subjects who have been able to discontinue the dextrose infusion and who are not on supplemental dextrose infusion at the end of the study will continue to be monitored without additional dextrose infusion for up to 3 hours after the end of the study drug infusion, or until blood glucose is $<$ 70 mg/dL (whichever comes first). In addition to blood glucose monitoring every 30 minutes and betahydroxybutyrate every 1 hr from a capillary sample, a venous sample will be drawn at the end of 3 hours (or when blood glucose $<$ 70 mg/dL, whichever comes first) for plasma insulin and glucose.
 10. Dose schemes.

Scheme #1 (completed as of date of Protocol Amendment 7): exendin-(9-39) infused for 12 hrs at a dose of 100 pmol/kg/min (0.02 mg/kg/hr).

Scheme #2 (completed as of date of Protocol Amendment 7): exendin-(9-39) infused for 12 hrs at a dose of 200 pmol/kg/min (0.04 mg/kg/hr).

Scheme #3 (completed as of date of Protocol Amendment 7): exendin-(9-39) infused for 6 hrs at a dose of 500 pmol/kg/min (0.1 mg/kg/hr).

Scheme #4 (new as of date of Protocol Amendment 7): Dose escalation will be done as described below:

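### Predicted neonatal Cmax and AUC are about 9-fold below what the protocol's own clearance gives, so every exposure-based safety margin is about 9-fold too large

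*Combined protocol and SAP*

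**What the plan says.** Section 1.4 (Dose Rationale and Risk/Benefits) reports a population PK analysis: "A linear two-compartment model best described the observed data". Its parameter table gives CL 11.9 L/hr, VC 8.57 L, Q 3.85 L/hr and Vp 7.00 L. For infants it states: "Typical clearance and elimination half-life for pediatric population with median weight 5 Kg are 1.64 L/hr and 0.94 hr, respectively". AUC and Cmax at the proposed doses were then "simulated using the developed population PK model".

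The next table gives medians of 1,000 simulated subjects, from Cmax 69.45 ng/mL and AUC 625.5 ng*hr/mL at 0.2 mg/kg/hr up to 2,083 and 18,764 at 6 mg/kg/hr. The Safety Margins table divides the rat and dog exposures at the no-adverse-effect level by these medians. Section 3.4 fixes the duration: "Exendin-(9-39) /vehicle will be infused intravenously over a period of 9 hours".

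The dose range itself runs "up to a maximum dose that is lower than the human equivalent (assuming 70% bioavailability) NOAELs from the toxicology studies in rats and dogs". For the dose-based margins, footnote b of the Safety Margins table says "For rat HED is 102 mg/kg/day; for dog HED is 117 mg/kg/day; calculations includes bioavailability of 70", and a column heading reads "Safety margin based on HED from rat (300 mg/kg/day". Section 1.2.3 says instead that the "no observed adverse effect levels (NOAELs) were 900 mg/kg/day in rats and at 300 mg/kg/day in dogs", and lists the human-equivalent doses as 116 and 102 mg/kg/day.

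**The concern.** In a linear model AUC equals dose divided by clearance. The clearance and the AUC table appear in the same section and are said to come from the same model, so one must give the other. They do not.

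The margins support a 30-fold escalation (0.2 to 6 mg/kg/hr) in infants from birth to 12 months. Section 5.4 leaves escalation to the investigator, the Safety Officer and the pharmacologist, and section 5.6.1 provides no DSMB. For cohort 4 the table tells them that AUC sits 13- to 18-fold below the animal no-effect exposure. The stated clearance says about 1.5- to 2-fold.

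There is also a practical risk in cohort 1. Observed levels near 610 ng/mL, set against a printed prediction of 69, could be misread as ninefold accumulation.

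**Working it through.** **1. The margin divisions are right.** From the printed exposures at 6 mg/kg/hr: 249,000/18,764 = 13.3; 340,500/18,764 = 18.1; 63,200/2,083 = 30.3; 49,500/2,083 = 23.8. The printed margins are 13, 18, 30 and 24. Any error therefore lies in the human exposures.

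**2. The 1.64 L/hr is not a misprint.** Assume a 70 kg reference subject, exponent 0.75 on CL and Q, and exponent 1 on the volumes. The protocol does not state this scaling. At 5 kg:

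- CL = 11.9 × (5/70)^0.75 = 1.644 L/hr; Q = 0.532 L/hr; VC = 0.612 L; Vp = 0.500 L.
- Rate constants: k10 = CL/VC = 2.686, k12 = Q/VC = 0.869, k21 = Q/Vp = 1.064, with sum s = 4.619 per hour.
- Slow rate = [s − √(s² − 4·k10·k21)]/2 = 0.736 per hour, so the half-life is 0.693/0.736 = 0.942 hr.

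These match the stated 1.64 L/hr and 0.94 hr.

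**3. Exposures from the stated clearance.** AUC = rate × 9 h × weight / CL, and plateau = rate × weight / CL, with weight 5 kg and CL 1.64 L/hr.

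| Dose (mg/kg/hr) | Cmax printed | Plateau recomputed | AUC printed | AUC recomputed |
|---|---|---|---|---|
| 0.2 | 69.45 | 610 | 625.5 | 5,488 |
| 0.6 | 208.3 | 1,829 | 1,876 | 16,463 |
| 2 | 694.5 | 6,098 | 6,255 | 54,878 |
| 6 | 2,083 | 18,293 | 18,764 | 164,634 |

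The ratio is 8.8 in every row. Nine hours is more than nine half-lives, so the plateau is reached. A numerical run of the two-compartment model gives 608 ng/mL at 9 hours for the lowest dose.

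**4. Margins (animal value / human value).**

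| Dose (mg/kg/hr) | AUC rat: printed → recomputed | AUC dog | Cmax rat | Cmax dog |
|---|---|---|---|---|
| 0.2 | 398 → 45 | 544 → 62 | 910 → 104 | 713 → 81 |
| 0.6 | 133 → 15 | 181 → 21 | 303 → 35 | 238 → 27 |
| 2 | 40 → 4.5 | 54 → 6.2 | 91 → 10 | 71 → 8.1 |
| 6 | 13 → 1.5 | 18 → 2.1 | 30 → 3.5 | 24 → 2.7 |

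**5. What the printed values would need.** 1.8 mg/kg divided by 625.5 ng*hr/mL is 2.88 L/hr/kg, or 14.4 L/hr at 5 kg. That exceeds the 11.9 L/hr population value.

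**6. Sensitivity.** With the scaling in step 2, the shortfall is 7.7-fold at 3 kg and 10.4-fold at 10 kg. Top-dose AUC margins run from 1.7 (rat) and 2.4 (dog) at 3 kg to 1.3 and 1.7 at 10 kg. Between-subject variation does not close the gap. The printed values are medians, and if the CL variance of 0.0722 is on the log scale, the 97.5th percentile of CL at 5 kg is 1.64 × exp(1.96 × √0.0722) = 2.78 L/hr, far below 14.4.

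**7. Species labels.** The Safety Margins headings give 300 mg/kg/day for rat and 900 for dog; section 1.2.3 gives the reverse. Footnote b has 102 for rat and 117 for dog; section 1.2.3, read in its rat-then-dog order, has 116 and 102. The printed margins follow footnote b: 102/54 = 1.9 and 117/54 = 2.2.

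**The case against.** - **The dose ceiling does not rest on these columns.** It is set by human-equivalent dose. The top dose totals 54 mg/kg, below 102, and the margins of 1.9 and 2.2 are printed in the same row. This stands: correcting the exposures does not breach the stated dose-setting rule. It does remove the impression that exposure adds a much wider margin.
- **The absolute margins depend on what the animal AUC covers.** Animals were dosed three times daily, and the documents do not say whether the AUC is per dose or per day. If it is per dose and the three doses are equal, the top-dose daily margins would be about 3 × 1.51 = 4.5 (rat) and 3 × 2.07 = 6.2 (dog). This stands as a condition on 1.5 and 2.1, and it means their closeness to the dose-based margins is not independent confirmation. The printed margins on that basis would be about 40 and 54, still about 9-fold too high.
- **The cause is unknown.** Treating 0.2 mg/kg as the whole 9-hour dose gives AUC 0.2 × 5/1.64 = 610 and a plateau of 610/9 = 68, within 3% of print. Unscaled CL of 11.9 L/hr at about 4.13 kg gives AUC 625 and a 9-hour level of 68.6, about 1% below the printed Cmax. The documents support neither over the other. The discrepancy does not depend on which is right.
- **Age.** Section 1.4 says the PK parameters also relate to age but gives no equation. However, 1.64 L/hr is stated as the typical paediatric value.
- **Levels are measured.** Sampling at 1, 5 and 9 hours and after the infusion would reveal the gap from cohort 1. However, section 5.4 does not list drug levels among the data reviewed before escalation.
- **Species labels.** The crossed daily doses are in the headings only, and they change no printed margin.

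**Conclusion.** The concern holds. The predicted Cmax and AUC in section 1.4 are 8.8-fold too low at 5 kg given the clearance stated beside them (7.7- to 10.4-fold over 3 to 10 kg under the assumed scaling), and all four exposure-margin columns are too large by the same factor. At 6 mg/kg/hr the AUC margins are about 1.5 (rat) and 2.1 (dog), not 13 and 18. The relative error rests only on the stated clearance, the 9-hour infusion and model linearity. The absolute margins also take the animal AUCs as tabulated.

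These are values for a typical infant. If 0.0722 is a log-scale variance, a 5 kg infant at the 2.5th percentile of clearance (0.97 L/hr) would reach a top-dose AUC of about 279,000 ng*hr/mL, above the tabulated rat value of 249,000. This does not show that the top dose is unsafe, and the dose-based margins are unchanged. It does show that the exposure evidence offered for that dose is wrong as printed. The plot of simulated exposures could not be checked.

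**What to change.** 1. Re-run the simulation with total dose = rate × 9 h and the stated clearance. State the scaling, any age equation and the weights used.
2. Reprint the Cmax/AUC table and the four exposure-margin columns. Check the figure against the new run and replace it if it carries the same error.
3. State whether the animal AUCs are per dose or per day, and put the margins on a matching basis.
4. Place each NOAEL and human-equivalent dose under the right species, and make sections 1.2.3 and 1.4 agree.
5. Give the corrected margins to the investigator, Safety Officer and pharmacologist, the IRB and the FDA. Whether the dose range still stands is their decision.
6. Add to section 5.4 a comparison of observed exendin-(9-39) levels with the corrected predictions at each cohort review.

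The cost is one run of an existing model and a correction by amendment. The stated margins become much less favourable.

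### The simulated infant exposures in section 1.4 conflict about 8.8-fold with the protocol's own pediatric clearance, and the AUC and Cmax safety margins inherit the conflict

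*Combined protocol and SAP*

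**What the plan says.** Section 1.4 (Dose Rationale and Risk/Benefits) describes the model: "A linear two-compartment model best described the observed data". For infants it gives: "Typical clearance and elimination half-life for pediatric population with median weight 5 Kg are 1.64 L/hr and 0.94 hr". The ranges of AUC and Cmax expected "with these doses were simulated using the developed population PK model". The medians over 1,000 simulated subjects are then tabulated at 0.2, 0.6, 2 and 6 mg/kg/hr.

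The table titled "Safety Margins based on dose and exposure (AUC)" divides rat and dog exposures by those medians. The escalation itself runs "up to a maximum dose that is lower than the human equivalent (assuming 70% bioavailability) NOAELs from the toxicology studies in rats and dogs".

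Two labels in the comparators are unclear.

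- **Animal AUC.** Section 1.2.3 ties the AUC to a single dose level ("in male and female rats at the 300 mg/kg/dose was 249,000" ng·hr/mL, with animals dosed three times daily). The exposure table in section 1.4 sets the same value beside the daily dose.
- **NOAELs.** Section 1.2.3 says "no observed adverse effect levels (NOAELs) were 900 mg/kg/day in rats and at 300 mg/kg/day in dogs". The margin table is headed "Safety margin based on HED from rat (300 mg/kg/day)" for rat and 900 mg/kg/day for dog.

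Section 5.4 lists adverse events, laboratory tests, ECGs and vital signs as the basis for escalation. It does not name drug levels. Section 3.4, item 13, already schedules exendin-(9-39) samples at 1, 5 and 9 hours and after the infusion.

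**The concern.** In a linear model, AUC is dose divided by clearance, so a stated clearance and a simulated AUC from the same model must agree. Here they do not. The discrepancy is a constant multiple across all four doses, which suggests one systematic cause rather than rounding.

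The affected figures are the exposure-based safety margins for a first escalation above 0.1 mg/kg/hr in infants under one year. Section 1.4 cites modeled PK as part of the basis for the new cohorts. Anyone reading the margin table sees 13- to 30-fold exposure margins at the top dose, far wider than the dose-based margins of 1.9 and 2.2. At the stated clearance, most of that extra margin disappears.

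**Working it through.** **Inputs.**

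- Section 1.4 text: clearance (CL) 1.64 L/hr and half-life 0.94 hr at 5 kg.
- Section 1.4 parameter table: CL 11.9 L/hr, VC 8.57 L, Q 3.85 L/hr, Vp 7.00 L, variance on CL 0.0722.
- Section 3.4, item 10: 9-hour infusions, total doses 1.8, 5.4, 18 and 54 mg/kg.
- Section 1.4 exposure table: simulated medians; rat Cmax 63,200 ng/mL and AUC 249,000 ng·hr/mL; dog 49,500 and 340,500.

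**1. Reproduce the printed margins (6 mg/kg/hr).** AUC: 249,000/18,764 = 13.3 and 340,500/18,764 = 18.1. Cmax: 63,200/2083 = 30.3 and 49,500/2083 = 23.8. These match the printed 13, 18, 30 and 24. The division is right, so the question is the denominators.

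**2. Clearance implied by the table.** AUC/Cmax = 625.5/69.45 = 9.01 hr, and likewise 18,764/2083 = 9.01 hr. Cmax is therefore the plateau of a 9-hour infusion. Clearance per kg = dose/AUC:

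- at 0.2 mg/kg/hr, 1.8/0.6255 = 2.88 L/hr/kg
- at 6 mg/kg/hr, 54/18.764 = 2.88 L/hr/kg

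At 5 kg this is 14.4 L/hr. The text gives 1.64 L/hr, or 0.328 L/hr/kg. Ratio: 14.4/1.64 = 8.8.

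**3. Which figure the parameter table supports.** Assume a 70 kg reference, clearances scaled by (5/70)^0.75 and volumes by 5/70; the protocol does not state the form. Then CL = 1.644, VC = 0.612, Q = 0.532 and Vp = 0.500, with a terminal half-life of 0.942 hr. Both stated pediatric values are recovered. The same parameters at 0.2 mg/kg/hr give 602 ng/mL at 5 h and 608 ng/mL at 9 h, against a tabulated Cmax of 69.45.

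**4. Can anything close the gap?**

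- Weight, with the same scaling: the factor is 7.4 at 2.5 kg and 10.4 at 10 kg.
- With CL fixed at 1.64 L/hr, the tabulated AUC would need a 0.57 kg infant.
- A variance of 0.0722 is about 27% CV, which cannot move a median 8.8-fold.
- CL of 11.9 L/hr left unscaled comes close: 11.9 × 0.6255/1.8 = 4.13 kg. At 4.13 kg the unscaled two-compartment model gives AUC 624.7 and an end-of-infusion level of 68.6, against 625.5 and 69.45. This is a possible cause to check; the protocol does not say it happened.

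**5. Exposures and margins at 1.64 L/hr and 5 kg.** AUC = rate × 9 × 5/1.64; plateau Cmax = rate × 5/1.64. Margins are rat/dog, with the printed margin in brackets.

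| mg/kg/hr | AUC, tabulated | AUC, recomputed | AUC margin | Cmax, recomputed | Cmax margin |
|---|---|---|---|---|---|
| 0.2 | 625.5 | 5,488 | 45/62 (398/544) | 610 | 104/81 (910/713) |
| 0.6 | 1,876 | 16,463 | 15/21 (133/181) | 1,829 | 35/27 (303/238) |
| 2 | 6,255 | 54,878 | 4.5/6.2 (40/54) | 6,098 | 10.4/8.1 (91/71) |
| 6 | 18,764 | 164,634 | 1.5/2.1 (13/18) | 18,293 | 3.5/2.7 (30/24) |

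**6. Per-dose reading of the animal AUCs.** If they cover one of three daily doses, the AUC margins could be up to three times wider: 13.6/18.6 at 2 mg/kg/hr and 4.5/6.2 at 6 mg/kg/hr. The Cmax margins do not depend on this.

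**7. Weight range at 6 mg/kg/hr (assumed 3 to 10 kg, weight-only scaling).** AUC is 144,528 at 3 kg and 195,286 at 10 kg. Per-day margins run from 1.72 to 1.28 (rat) and 2.36 to 1.74 (dog). Multiplied by 3 for the per-dose reading, they run from 5.2 to 3.8 and 7.1 to 5.2.

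**The case against.** The arithmetic of the conflict is not in dispute; its weight is. The ceiling was set by dose: 102/54 = 1.9 (rat) and 117/54 = 2.2 (dog), with no use of the simulation. All recomputed typical-infant margins stay above 1. Toxicology was benign and the NOAELs were the top doses of the 28-day studies, so the true distance to toxicity may be larger. Section 5.4 bases escalation on observed safety data, not on predicted margins, and its list of findings is open. The pharmacologist already sits on the panel, and the Data Safety Monitoring Plan, which is not in the available text, may already call for a PK review. Drug levels may also be sparse, because section 3.4 lets a subject continue without them when blood-drawing lines are difficult. The scaling form is inferred, age is also named as a covariate, and the simulation plots are not available, so the error may lie in the table alone.

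Much of this stands. It rules out a claim of breach or of a wrong dose ceiling, and it makes the section 5.4 change an option rather than a correction. The swapped headings have no numerical effect, since the printed dose-based margins come from the footnote values of 102 and 117 mg/kg/day. The objection does not rescue the exposure table. The 8.8-fold gap at 5 kg follows from the stated clearance and linearity alone, without any scaling assumption.

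**Conclusion.** The concern holds. Section 1.4 gives two infant clearances that differ about 8.8-fold, one stated and one implied by its exposure table. The parameter table supports the stated one. Unless 1.64 L/hr is itself wrong, the printed AUC and Cmax margins are too wide by that factor at every dose. On the Cmax comparison, the top-dose margins fall to 3.5 (rat) and 2.7 (dog). On AUC they fall to 1.5 and 2.1 on the per-day reading, or up to 4.5 and 6.2 on the per-dose reading. At 2 mg/kg/hr every margin remains above 4.

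The core result needs only linear PK, the stated clearance and the 5 kg weight. The support from the parameter table and the weight-range figures rest on the inferred 70 kg scaling. The consequence is lost margin in a safety rationale for infants, not a demonstrated overexposure. It should be corrected, but it does not by itself call for a lower ceiling.

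**What to change.** Before Scheme 4 dosing begins, or before the next escalation if it has begun:

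1. Reconcile the section 1.4 exposure table (and the accompanying simulation plots) with the clearance of 1.64 L/hr. Check first whether clearance was scaled to infant weight in the simulation. Then restate the AUC and Cmax margins.
2. State whether the animal AUCs are per dose or per day.
3. Correct the NOAEL headings in the margin table to rat 900 and dog 300 mg/kg/day. Align the human-equivalent doses in section 1.2.3, which follow a rat-then-dog sentence as 116 then 102, with the margin-table footnote (rat 102, dog 117).

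As an addition to section 5.4, or by reference if the Data Safety Monitoring Plan already covers it: before each step up, and above all before 6 mg/kg/hr, the investigator, Safety Officer and pharmacologist compare the available 5 h and 9 h levels with the corrected prediction and update the next dose's margin. Cohort 1 would separate the two clearances clearly, at about 69 versus about 608 ng/mL at 9 h. The team should set any deviation trigger.

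Items 1 to 3 are desk work: check and, if needed, rerun the existing simulation, then reissue two tables and align one sentence. The section 5.4 addition uses samples already scheduled. Its cost is a possible wait for assay results before 0.6, 2 and 6 mg/kg/hr; the documents do not give the turnaround time.
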